## 14 ADMINISTRATIVE AND ETHICAL CONSIDERATIONS

### 14.1 Regulatory and Ethical Compliance

This protocol was designed and will be conducted and reported in accordance with the International Conference on Harmonization (ICH) Harmonized Tripartite Guidelines for Good Clinical Practice, the Declaration of Helsinki, and applicable federal, state, and local regulations.

### 14.2 DUHS Institutional Review Board and DCI Cancer Protocol Committee

The protocol, informed consent form, advertising material, and additional protocol-related documents must be submitted to the DUHS Institutional Review Board (IRB) and DCI Cancer Protocol Committee (CPC) for review. The study may be initiated only after the Principal Investigator has received written and dated approval from the CPC and IRB.

The Principal Investigator must submit and obtain approval from the IRB for all subsequent protocol amendments and changes to the informed consent form. The CPC should be informed about any protocol amendments that potentially affect research design or data analysis (i.e. amendments affecting subject population, inclusion/exclusion criteria, agent administration, statistical analysis, etc.).

The Principal Investigator must obtain protocol re-approval from the IRB within 1 year of the most recent IRB approval. The Principal Investigator must also obtain protocol re-approval from the CPC within 1 year of the most recent IRB approval, for as long as the protocol remains open to subject enrollment.

### 14.3 Informed Consent

The informed consent form must be written in a manner that is understandable to the subject population. Prior to its use, the informed consent form must be approved by the IRB.

The Principal Investigator or authorized key personnel will discuss with the potential subject the purpose of the research, methods, potential risks and benefits, subject concerns, and other study-related matters. This discussion will occur in a location that ensures subject privacy and in a manner that minimizes the possibility of coercion. Appropriate accommodations will be made available for potential subjects who cannot read or understand English or are visually impaired. Potential subjects will have the opportunity to contact the Principal investigator or authorized key personnel with questions, and will be given as much time as needed to make an informed decision about participation in the study.

Before conducting any study-specific procedures, the Principal Investigator must obtain written informed consent from the subject or a legally acceptable representative. The original informed consent form will be stored with the subject's study records, and a copy of the informed consent form will be provided to the subject. The Principal Investigator is responsible for asking the subject whether the subject wishes to notify his/her primary care physician about participation in the study. If the subject agrees to such notification, the Principal Investigator will inform the subject's primary care physician about the subject's participation in the clinical study.

#### **14.4 Study Documentation**

Study documentation includes, but is not limited to, source documents, case report forms (CRFs), monitoring logs, appointment schedules, study team correspondence with sponsors or regulatory bodies/committees, and regulatory documents that can be found in the DCI-mandated "Regulatory Binder," which includes, but is not limited to, approved protocol versions, approved informed consent forms, FDA Form 1572s, and CAP and CLIA laboratory certifications.

Source documents are original records that contain source data, which is all information in original records of clinical findings, observations, or other activities in a clinical trial necessary for the reconstruction and evaluation of the trial. Source documents include but are not limited to hospital records, clinical and office charts, laboratory notes, memoranda, subjects' diaries or evaluation checklists, pharmacy dispensing records, recorded data from automated instruments, copies or transcriptions certified after verification as being accurate copies, microfiches, photographic negatives, microfilm or magnetic media, x-rays, subject files, and records kept at the pharmacy, at the laboratories and at medico-technical departments involved in the clinical trial. DUHS utilizes Epic Maestro Care as an electronic health record. When possible, the original record should be retained as the source document. However, a photocopy is acceptable provided that it is a clear, legible, and an exact duplication of the original document.

#### **14.5 Privacy, Confidentiality, and Data Storage**

The Principal Investigator will ensure that subject privacy and confidentiality of the subject's data will be maintained. Research Data Security Plans (RDSPs) will be approved by the appropriate institutional Site Based Research group.

To protect privacy, every reasonable effort will be made to prevent undue access to subjects during the course of the study. Prospective participants will be consented in an exam room where it is just the research staff, the patient and his family, if desired. For all future visits, interactions with research staff (study doctor and study coordinators) regarding research activities will take place in a private exam room in Duke Cancer Center Clinic 3-1. All research related interactions with the participant will be conducted by qualified research staff who are directly involved in the conduct of the research study.

To protect confidentiality, subject files in paper format will be stored in secure cabinets under lock and key accessible only by the research staff. Subjects will be identified only by a unique study number and subject initials. Electronic records of subject data will be maintained using a dedicated 21 CFR Part 11 compliant database, which is housed in an encrypted and password-protected on a secure network drive. Access to electronic databases (without edit rights) will be limited to the PI, the study coordinator, and the statistical team. The only personnel with both access and edit rights to the electronic databases are the data management team,

including the clinical trials manager. The security and viability of the IT infrastructure will be managed by the DCI and/or Duke Medicine.

Upon completion of the study, research records will be archived and handled per DUHS HRPP policy, i.e. all files and documents that relate to the protection of human research participants are retained for at least 6 years following study completion (see Section 14.8 below for other study document storage guidelines).

Subject names or identifiers will not be used in reports, presentations at scientific meetings, or publications in scientific journals.

## **14.6 Data and Safety Monitoring**

Data and Safety Monitoring will be performed in accordance with the DCI Data and Safety Monitoring Plan. For a more detailed description of the DSMP for this protocol, refer to the Safety Monitoring and Reporting section and the Quality Control and Quality Assurance section.

## **14.7 Protocol Amendments**

All protocol amendments must be initiated by the Principal Investigator and approved by the IRB prior to implementation. IRB approval is not required for protocol changes that occur to protect the safety of a subject from an immediate hazard. However, the Principal Investigator must inform the IRB and all other applicable regulatory agencies of such action immediately.

Though not yet required, the CPC should be informed about any protocol amendments that potentially affect research design or data analysis (i.e. amendments affecting subject population, inclusion/exclusion criteria, agent administration, etc.).

## **14.8 Records Retention**

The Principal Investigator will maintain study-related records for the longer of a period of:

- At least two years after the date on which a New Drug Application is approved by the FDA (if an IND is involved)
- At least two years after formal withdrawal of the Duke IND associated with this protocol (if an IND is involved)
- At least six years after study completion (Duke policy)

[figure not shown]

## 16 APPENDICES

### 16.1 Appendix A

#### DukeMedicine Guidelines for Management of Cutaneous Toxicity for Patients Receiving Epidermal Growth Factor Receptor

\*The use of topical steroids should be employed in a pulse manner based on your provider's guidelines.

## 16.2 Appendix B

**Name: BTC Imaging SOP- Procedures for Provider Reading of MRIs and CTs**

**Effective Date: 4/2012**

**Review/Revision History:**

**Definitions:**

**MRI** stands for magnetic resonance imaging with and/or without contrast

**CT** stands for computed tomography with and/or without contrast

**Radiation therapy (RT)** means treatment of the patient's tumor with radiation treatment, typically for about 6 ½ weeks. It may include stereotactic radiosurgery, which is a nonsurgical RT technique that delivers ionizing radiation to the tumor. **Pseudoprogression** means a transient increase in contrast-enhancement on MRI without true tumor progression

**Pseudoresponse** means marked decrease in contrast enhancement possibly due to anti-angiogenic therapy

**Non-enhancing disease progression** means progression of the tumor with components that are non-enhancing on MRI

**Anti-angiogenic agents** means a drug or substance inhibiting the growth of blood vessels

**Seizure** means any episode, caused by abnormal electrical conduction in the brain, resulting in the abrupt onset of transient neurologic symptoms

**Steroids** means a group of drugs that includes the corticosteroids, similar to hormones produced by the adrenal glands

**Immunotherapy** means treatment of disease by inducing, enhancing, or suppressing an immune response

**FLAIR** stands for fluid-attenuated inversion recovery [image sequences]

**RANO** stands for the Response Assessment in Neuro-Oncology (RANO)

**1. Determine Patient Background Information**

- A. Determine the patient's medical history.
- B. Has the patient had prior surgery?

C. Has the patient had Gliadel (carmustine) wafers placed into the resection cavity? Note: Be careful with therapeutic effect

D. Has the patient undergone radiation therapy or stereotactic radiosurgery?

Note: Be careful with pseudoprogression

E. Has the patient taken any anti-angiogenic agents, such as bevacizumab (Avastin), sunitinib (Sutent), or cediranib (Recentin)? Note: Be careful with pseudoresponse and non-enhancing disease progression

F. Has the patient experienced seizure activity recently?

G. Has the patient tapered up or down in their dose of steroids? H. Has the patient undergone any form of immunotherapy?

**2. Pick the right date of previous MRI/CT to which you want to compare the new MRI**

- A. For high grade patients off therapy, go back to the MRI when they stopped therapy.
- B. For low grade patients off therapy, go back to baseline MRI. The best baseline MRI is normally 2-

4 months post-operative (post-operative changes must have resolved and at the nadir of cavity collapse).

[figure not shown]
C. For patients on treatment, compare to baseline (response) and to nadir (progression).

[figure not shown]

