#### 7.1.1 Dose Modification

For subjects receiving 18 mg/kg, the dose of Sym004 may be reduced by up to two dose levels, if the subject experiences grade 3-4 non-hematologic toxicities secondary to Sym004, e.g. skin toxicities, electrolyte disturbances, and gastrointestinal symptoms, or grade 4 neutropenia or thrombocytopenia. Following the initial dose of 18 mg/kg every 2 weeks, if the subject needs to have their dose of Sym004 reduced due to an aforementioned toxicity, then their next dose will be 15 mg/kg every 2 weeks. If another reduction in dose is necessary, the subsequent dose will be 12 mg/kg every 2 weeks. If dose reduction is required more than two times, the patient will be removed from the study.

#### 7.1.2 Dose Modification Post-Amendment 31

For subjects receiving 24 mg/kg, the dose of Sym004 may be reduced by up to two dose levels, if the subject experiences grade 3-4 non-hematologic toxicities secondary to Sym004, e.g. skin toxicities, electrolyte disturbances, and gastrointestinal symptoms, infusion-related reactions, or grade 4 neutropenia or thrombocytopenia. Exceptions to this dose reduction include grade 3 nausea, vomiting, diarrhea or fatigue lasting  $\leq$  5 days with supportive care or grade 3 asymptomatic electrolyte abnormalities. Following the initial dose of 24 mg/kg every 2 weeks, if the subject needs to have their dose of Sym004 reduced due to an aforementioned toxicity, then their next dose will be 18 mg/kg every 2 weeks. If another reduction in dose is necessary, the subsequent dose will be 15 mg/kg every 2 weeks. If dose reduction is required more than two times, the patient will be removed from the study.

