## 10.6 Follow-up Period

Patients will be followed for safety a minimum of 30 days after last dose of study drug, and also followed for any new and/or unresolved serious adverse events considered related to study therapy. Once "off study," subjects will be followed for progression (for patients who came off study prior to disease progression) and survival status (all patients) at least 1 year, if possible. Subjects not returning to Duke will be contacted via phone or information will be obtained through their local physician every 3 months to determine time of progression or survival.

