### **10.9.3 Radiographic Review**

The RANO criteria will be used to determine progression and pseudo-progression, as defined by Wen et al., 2010 (see Appendix B).

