Stable Disease (SD)	SPD < 50% decrease to < 25% increase
Progressive Disease (PD)	SPD increased by $\geq 25\%$ from nadir value (smallest seen during the trial) (look out for pseudoprogression)
Unable to Assess (UA)	One or more of the target lesions cannot be evaluated because of technical factors

iv. Assessed subjectively

Response	Definition
Complete Response (CR)	All enhancing non-target lesions have disappeared completely
Incomplete Response /Stable Disease (IR/SD)	Enhancing lesions present, and stable or decreased in size compared to prior imaging
Progressive Disease (PD)	Unequivocal progression of enhancing lesions (see below)

Unable to Assess (UA)	Unable to evaluate enhancing lesions because of technical factors
-----------------------	---

- I. Pseudoresponse
  - i. Anti-angiogenic drug effects can look like response
  - ii. Apparent response may appear within 4 weeks
  - iii. This should be confirmed with follow-up imaging 4+ weeks later
- J. Pseudoprogression
  - i. Enhancement that looks like tumor growth but isn't
  - ii. Radiation effect can look like tumor
  - iii. Apparent PD within 12 weeks of RT
  - iv. Call it pseudoprogression (psPD) initially v. Re-evaluate at next imaging visit
  - vi. If further increase, call it PD on the first visit vii. If stable or decreased, psPD is confirmed
  - viii. Do not consider baseline for choosing nadir – looking for progression
  - ix. Still use baseline when looking for response x. New lesions
  - xi. PD within the 12 weeks of completion of chemoradiation can only be assigned if:
    - a. Majority of the new enhancement is outside of the radiation field
    - OR
    - b. Pathologic confirmation of progressive disease (tricky)
    - c. Lesion continues to enlarge

Baseline	Visit 1 (8 weeks)	Visit 2 (16 weeks)	Visit 3 (24 weeks)
100	140 psPD	120 SD	150 → PD 130 → SD 65 → SD 45 → PR

K. RANO – From lesion to timepoint (radiological)

Target Lesions	Enhancing Non-Target Lesions	FLAIR/T2 Lesions	New Lesions	Radiological Timepoint Response
CR	CR	Not worse	No	CR
CR	IR/SD or UA	Not worse	No	PR
PR	Any non-PD or UA	Not worse	No	PR

SD	Any non-PD or UA	Not worse	No	SD
UA	Any non-PD	Not worse	No	UA
PD	Any	Any	Yes/No	PD
Any	PD	Any	Yes/No	PD
Any	Any	Any	Yes	PD
Any	Any	Worse	Yes/No	PD
NA*	CR	Not worse	No	CR
NA*	SD	Not worse	No	SD
NA*	NA**	Not worse	No	No Change
NA* = No target lesions identified at baseline. NA** = No non-target lesions identified at baseline				

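### Appendix B gives two unreconciled reference scans for judging progression after Sym004 stops; following item 2.A can delay target-lesion PD and so can raise PFS6

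*Combined protocol and SAP*

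**What the plan says.** - **Which criteria govern.** Section 10.9.3: "The RANO criteria will be used to determine progression and pseudo-progression", with a pointer to Appendix B. The appendix is an imaging procedure of the brain tumor center, effective 2012, that also covers low-grade patients.
- **Reference scan off therapy.** Appendix B item 2.A: "For high grade patients off therapy, go back to the MRI when they stopped therapy". All subjects have grade IV disease (Section 3.2), so all are high grade.
- **Reference scan on therapy.** Item 2.C: "For patients on treatment, compare to baseline (response) and to nadir (progression").
- **PD definition.** The target-lesion table in the same appendix calls PD when SPD has risen by at least 25% "from nadir value (smallest seen during the trial"). It makes no distinction between on and off therapy.
- **Who reaches the off-therapy rule.** Sections 7.1.1 and 7.1.2 both state: "If dose reduction is required more than two times, the patient will be removed from the study". Section 10.8.1 adds voluntary withdrawal and intolerable symptoms.
- **What happens to them.** Section 13.1 analyses everyone who received any Sym004. Under Section 10.6, after leaving the study, "subjects will be followed for progression (for patients who came off study prior to disease progression"), for at least a year where possible. For those who do not come back: "Subjects not returning to Duke will be contacted via phone or information will be obtained through their local physician every 3 months".
- **Endpoint.** Section 13.4.1 counts patients alive and progression-free 6 months after starting Sym004. Stopping treatment is neither an event nor a reason for censoring (Sections 3.4 and 13.5.2).

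**The concern.** The primary endpoint depends on when progression is called, and the appendix gives two answers to which scan the new one is compared with. A reader who follows item 2.A for a patient who has stopped Sym004 uses a later reference scan than the PD row does. The nadir is by definition the smallest value, so the stop scan can equal it or exceed it but never fall below it. Item 2.A can therefore only leave the SPD threshold unchanged or raise it. Any resulting error delays PD and can turn a 6-month failure into a success, which is the unsafe direction for a single-arm design tested against a fixed historical rate. The choice of reference would also depend on treatment status, which the drug itself can affect, and PFS6 is to be reported for each dose level.

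**Working it through.** **1. The plan's own figures.** No figure in the documents describes the off-therapy reading rule, so I reproduced the design that PFS6 feeds. For Cohort 1 at 24 mg/kg (Section 13.8.2), stage 1 has 19 patients and stops at 3 or fewer successes. Stage 2 adds 17, and the treatment is rejected at 10 or fewer of 36.

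- Probability of early termination: PET = P(X1 ≤ 3), X1 ~ Bin(19, 0.20), = 0.4551 (plan 0.455).
- Expected N = 19 + (1 − 0.4551) x 17 = 28.26 (plan 28.26).
- Type I error = sum over x = 4 to 19 of P(X1 = x) x P(X2 ≥ 11 − x), X2 ~ Bin(17, 0.20), = 0.0861 (plan 0.086).
- Type II error, same sum at 0.40: 1 − 0.9024 = 0.0976 (plan 0.098).

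**2. The two thresholds.** Let N be the nadir SPD and S the SPD at the stop scan.

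- PD row: PD at 1.25 x N.
- Item 2.A: PD at 1.25 x S, that is 1.25 x (S/N) relative to the nadir.

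Suppose the patient has not met PD by SPD when stopping, the nadir was reached by the stop scan, and the pseudoprogression exception is not in play. S/N then lies between 1.00 and just under 1.25.

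| S/N at stop | PD threshold under 2.A, relative to nadir |
|---|---|
| 1.00 | 1.25 (no difference) |
| 1.10 | 1.375 |
| 1.20 | 1.50 |
| limit 1.25 | 1.5625 |

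The extra growth that item 2.A tolerates is therefore between 0 and just under 1.5625 − 1.25 = 0.3125 of the nadir, about 31 points. If SPD fell further after stopping, the nadir would move down and the gap could be wider. The documents give no data on that case.

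**3. Example (invented values).** Baseline 100, nadir 50, stop scan 60, next scan 72. The stop scan is not PD: 60/50 = 1.20. The next scan gives 72/50 = 1.44 (+44%, PD) by the PD row, and 72/60 = 1.20 (+20%, SD) by item 2.A.

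**4. How many patients could be affected.** Section 7.2 describes the first 19 patients at 18 mg/kg: 16 came off for progression before 6 months and 1 completed 6 months of therapy. That leaves 19 − 16 − 1 = 2 (10.5%) undescribed, and nothing says that either stopped early without progression. There is no figure for 24 mg/kg.

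**5. Why a few would matter.** Let e be the assumed share of patients wrongly counted as progression-free at 6 months. Running the Cohort 1 rule at 0.20 + e gives:

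| e (assumed) | False-positive rate |
|---|---|
| 0 | 0.086 |
| 1 point | 0.113 |
| 2 points | 0.145 |
| 3 points | 0.182 |
| 5 points | 0.268 |

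Three points is about one patient (0.03 x 36 = 1.08). In Cohort 2, stage 1 is passed with a single success among 12. At a true rate of 3% that has probability 1 − 0.97^12 = 0.31, and with 2 points of misclassification 1 − 0.95^12 = 0.46. These are sensitivity figures, not estimates of e.

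**The case against.** The strongest reply is that nothing says item 2.A overrides the PD definition. Section 10.9.3 names RANO, the PD row is explicit about the nadir, and item 2 is only a scan-selection step in a general clinic procedure. A careful reader could apply the PD row throughout. Nor is off therapy defined as off Sym004: a patient who starts another treatment might be read under item 2.C. The figures that accompany item 2 were not available for this check. All of this is fair, and it is why the point is a failure to reconcile two rules rather than proof that the wrong one will be used. It does not remove the conflict, because item 2.C confines the nadir to patients on treatment and no sentence exempts trial subjects from item 2.A.

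The second reply also largely stands. A false success needs a patient who stops before month 6 without PD, has SPD already above nadir, and then stays between the two thresholds through month 6. That patient must also have no new lesion, no T2/FLAIR worsening, no non-target progression and no clinical decline. With MRIs every 8 weeks, few scans before month 6 can produce that sequence.

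Two stronger inferences are tempting and unsupported:

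- **That up to 56% growth goes uncounted.** Growth below 25% is not PD under either rule, so the excess is at most about 31 points of nadir in the setting of step 2.
- **That a more toxic dose will show longer PFS.** Removal under Sections 7.1.1 and 7.1.2 comes only when a third reduction is needed, and 2 of the first 19 patients at 18 mg/kg had grade 3 skin toxicity. The documents contain no rate of stopping before progression at either dose.

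**Conclusion.** The inconsistency is real and affects the primary endpoint. For a patient who stops Sym004 before PD with SPD above nadir, item 2.A raises the target-lesion threshold from 1.25 to as much as just under 1.56 x nadir, given a nadir reached by the stop scan. For a patient whose stop scan is the nadir it changes nothing. Any error can only delay PD, so it can raise PFS6 and cannot lower it.

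A reader might go on to conclude that PFS6 is inflated, or put a number of percentage points on it. The documents do not allow that. They do not show which rule readers follow, how many patients stop before progression, or how SPD moves afterwards, and at most 2 of the first 19 patients are even candidates. The number affected is probably small. The point still deserves correction because the decision rules turn on few patients and Cohort 1 has little room between its type I error of 0.086 and the 0.10 target.

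**What to change.** Add to Appendix B, item 2, wording to this effect:

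> For all PFS and PFS6 readings in this trial, whether the subject is on or off Sym004, progression is judged against the nadir SPD, counting baseline as a candidate for the nadir except where the pseudoprogression rules in this appendix remove it. Response is judged against baseline. Item 2.A does not apply to trial subjects.

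Apply this to the off-treatment scans that are available, and report how many patients stopped Sym004 before progression within 6 months so that the size of the issue can be seen.

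The cost is a brief amendment and some re-reading. It needs no new scans and changes no stated design figure. It will not standardise progression that reaches the trial only by telephone or through a local physician, and Section 10 sets no MRI schedule after the End of Treatment visit, so for some patients there may be no scan to re-read.
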